The research questions motivating this study relate to how well the distribution of the DHCP letter has proceeded in the early post-launch period and how well that communication material conveys the most significant risks of Humulin[®] R U-500 KwikPen[®] to prescribers. The study also evaluates prescriber understanding about important patient education about those risks. As noted above, this early evaluation focuses on process measures related to reaction, learning, and planned behavior.

The primary study objective is to evaluate the impact of the DHCP letter on prescriber understanding about the risk of hypoglycemia and educational points to be emphasized in discussion with patients.

Retention and comprehension by HCPs of the following specific key safety messages will be tested in line with this objective. Specifically, HCPs should:

- only consider prescribing Humulin[®] R U-500 KwikPen[®] to patients needing more than 200 units of insulin per day.
- specify the prescribed dose in units of insulin (5-unit increments) on the prescription.
- inform patients of their dose in units of insulin.
- educate patients that no dose conversion is needed with Humulin[®] R U-500 KwikPen[®] and that the dose window shows the number of units to be injected.
- educate patients not to withdraw Humulin[®] R U-500 insulin from the KwikPen[®] with a syringe.
- instruct patients to maintain backup Humulin® R U-500 KwikPen®.
- instruct patients in the event of a malfunction, to use their backup pen or contact a pharmacist, healthcare professional, or The Lilly Answers Center for more information at [name].
- teach patients not to count clicks to determine their dose when using Humulin[®] R U-500 KwikPen[®].

The secondary objectives include

- assessing the proportion of HCPs receiving and reading the DHCP letter and their reactions to the risk mitigation communication content.
- querying prescriber intentions regarding patient education around safe use of the Humulin[®] R U-500 KwikPen[®].

6 Research Method

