6.7.4 Primary Objectives and Endpoints

Frequencies and percentages, along with 95% CIs will be used to assess HCP retention and comprehension of the risks associated with the Humulin® R U-500 KwikPen®. The denominator will be the number of HCPs who complete the survey. Specifically, primary endpoints are the proportion of those correctly answering each of the following statements. Response options are either True/False or multiple choice.

- It is appropriate to prescribe Humulin[®] R U-500 KwikPen[®] to patients needing more than 200 units of insulin per day.
- It is important to clearly specify the units of insulin (5-unit increments) on the prescription when prescribing Humulin® R U-500 KwikPen®
- When prescribing Humulin[®] R U-500 KwikPen[®] it is important to inform patients of their dose in units of insulin.
- When administering the Humulin[®] R U-500 KwikPen[®], patients do not need to convert the dose since the dose window shows the number of units to be injected.
- It is important to instruct your patients that they should always have a backup Humulin[®] R U-500 KwikPen[®] available.
- It is important to instruct your patients to not count clicks to audibly verify the correct dose.
- In the event of a Humulin[®] R U-500 KwikPen[®] malfunction, it is appropriate for patients to use a backup pen, call their healthcare provider or pharmacist, or call the Lilly Answer Center; but it is not appropriate to use a syringe to withdraw insulin from the injector.

The RMiP will be considered effective if the majority of HCPs demonstrate they are aware of the key safety messages communicated for Humulin[®] R U-500 KwikPen[®] by correctly answering these statements.

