6.10 Measures to Minimize Bias

HCPs completing the screener and meeting the Humulin[®] R U-500 KwikPen[®] survey eligibility requirements will be directed to participate in the online survey. Survey biases will be minimized through carefully constructed, non-leading survey questions, and a thorough internal validation process. Online forms will be programmed such that HCPs have access to only one survey question at a time; once a question is submitted, HCPs do not have the option of revisiting it, i.e., the back button is disabled. Lists of response options will be randomized to minimize the potential for positional bias.

Correct responses will be provided to the physicians following recording of their response, allowing for feedback on performance and reinforcing correct information and/or best clinical practice.

7 Protection of Human Subjects

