15. Please answer True, False, or I don't know for each of the following statements regarding Humulin® R U-500 KwikPen®.

		True	False	I don't know
a	It is appropriate to prescribe Humulin® R U-500 KwikPen® to	0	0	0
	patients needing more than 200 units of insulin per day.	1	2	3
b	It is important to clearly specify the units of insulin (5-unit	0	0	0
	increments) on the prescription when prescribing Humulin® R U-	1	2	3
	500 KwikPen [®] .			
c	When prescribing Humulin [®] R U-500 KwikPen [®] it is important to	0	0	0
	inform patients of their dose in units of insulin.	1	2	3
d	When administering the Humulin [®] R U-500 KwikPen [®] , patients do	0	0	0
	not need to convert the dose since the dose window shows the	1	2	3
	number of units to be injected.			
e	It is important to instruct your patients that they should always have	0	0	0
	a backup Humulin [®] R U-500 KwikPen [®] available.	1	2	3
f	It is important to instruct your patients not to count clicks to	0	0	0
	determine their dose.	1	2	3

[PROGRAMMING NOTE: Randomize the list above a-f.]

16. In the event of a Humulin® R U-500 KwikPen® malfunction, what would you instruct patients to do? (please select all that apply)

□ Use a backup pen
□ Use a syringe to withdraw the insulin from the KwikPen®
□ Contact a pharmacist or healthcare professional
□ Contact the Lilly Answer Center for more information at [name]

17. My answers to the true/false statements earlier about the Humulin® R U-500 KwikPen® were based on...(choose all that apply)

□ Professional knowledge about the use of human insulin products.
□ Previous experience with KwikPen® technology in other Lilly products such as Humalog □ Familiarity with the Humulin® R U-500 KwikPen® package insert.
□ Knowledge gained from interaction with Lilly's sale representative.
□ Knowledge gained from the Humulin Dear Health Care Provider letter.

[PROGRAMMING NOTE: Randomize the response options above 1-7.]

Study Protocol for Humulin® R U-500 KwikPen®

₆ □ Guessing

7 □ Online information

labeling.

18. Did you read the Dear Health Care Provider letter provided to you by Eli Lilly and Company on "Important Prescribing Information" for the Humulin® R U-500 KwikPen® (insulin human)?
₁ □ Yes
₂ □ No
3 □ I don't recall
[PROGRAMMING NOTE: If participant answers "1" then go to following items based on
agreement scales. If participant answers "2" or "3" skip the following series of 4 items identified under 19 and go to the following question.]

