Appendix III Thank - You Letter and Correct Survey Responses

Dear [FIRST NAME] [LAST NAME]:

On behalf of Eli Lilly and Company, the maker of $Humulin^{@}R$ U-500 $KwikPen^{@}$, we want to thank you for taking part in the $Humulin_{@}R$ U-500 $KwikPen_{@}Survey$.

Additionally, to ensure that survey participants have accurate information about the risks of Humulin[®] R U-500 KwikPen[®], we have provided links to the following two documents:

- A copy of the correct answers to the survey questions about the Humulin® R U-500 KwikPen® key safety messages
- A copy of the Humulin[®] R U-500 KwikPen[®] Dear Health Care Provider (DHCP) letter.

<Insert the correct answers to the survey questions link>

<Insert DHCP letter link>

Sincerely,

The Humulin® R U-500 KwikPen® Survey Team

Correct Survey Responses to Humulin® R U-500 KwikPen®

15. Please answer True, False, or I don't know for each of the following statements regarding Humulin® R U-500 KwikPen®.

		True	False	I don't know
a	It is appropriate to prescribe Humulin [®] R U-500 KwikPen [®] to patients needing more than 200 units of	•	0	0
b	insulin per day. It is important to clearly specify the units of insulin (5-unit increments) on the prescription when prescribing Humulin [®] R U-500 KwikPen [®] .	•	0	0
c	When prescribing Humulin [®] R U-500 KwikPen [®] it is important to inform patients of their dose in units of insulin.	•	0	0
d	When administering the Humulin [®] R U-500 KwikPen [®] , patients do not need to convert the dose since the dose window shows the number of units to be injected.	-	0	0
e	It is important to instruct your patients that they should always have a backup Humulin [®] R U-500 KwikPen [®] available.	-	0	0
f	It is important to instruct your patients to not count clicks to determine their dose.		0	0

16. In the event of a Humulin[®] R U-500 KwikPen[®] malfunction, what would you instruct patients to do? (please select all that apply)

	U	se	a	bac.	kup	pen
--	---	----	---	------	-----	-----

[☐] Use a syringe to withdraw the insulin from the KwikPen®

[■] Contact a pharmacist or healthcare professional

[■] Contact The Lilly Answer Center for more information at [name]

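### Q15a and the first primary endpoint leave out the restriction in the Section 5 key message, so they cannot detect a prescriber who ignores it; secondarily, all six Q15 items are keyed True, so any tendency to agree raises percent correct

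*Protocol*

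**What the plan says.** **The message.** Section 5 lists the key safety messages to be tested. The first is that HCPs should "only consider prescribing Humulin[®] R U-500 KwikPen[®] to patients needing more than 200 units of insulin per day". In the letter (Appendix I), the Dosage and Administration part of the safety information also carries the word ONLY, in capitals. The Prescriber Actions bullet of the same letter omits it.

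**The item.** The first primary endpoint in 6.7.4 reads "It is appropriate to prescribe Humulin[®] R U-500 KwikPen[®] to patients needing more than 200 units of insulin per day". Q15a in Appendix II has the same wording, and Appendix III keys it True.

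**The set.** Q15 opens with "Please answer True, False, or I don't know for each of the following statements regarding" the product and lists six statements, a to f. Under "Correct Survey Responses to Humulin® R U-500 KwikPen", Appendix III leaves False and I don't know open for all six. Item f, for example, is "It is important to instruct your patients to not count clicks to determine their dose". In the copy read, the True cell of item f is blank, but its two open alternatives and the Section 5 message on clicks leave no reading other than True.

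**Scoring and decision.** Section 6.7 counts I don't know as incorrect. Section 6.7.4 makes the proportion correct on each statement a primary endpoint and calls the risk minimization plan effective if the majority of HCPs answer correctly.

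**Safeguards.** Appendix II has "PROGRAMMING NOTE: Randomize the list above a-f". Section 6.10 adds randomised response options against positional bias and states: "Survey biases will be minimized through carefully constructed, non-leading survey questions, and a thorough internal validation process". Q17 asks what the true/false answers were based on and offers guessing as one choice.

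**The concern.** A knowledge item should separate those who hold the message from those who do not. Q15a asks whether a use inside the restriction is acceptable, whereas the message concerns use outside it. Both kinds of prescriber can truthfully tick True.

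The other five items are also true as worded, so a respondent who ticks True throughout scores 6 of 6. Randomising the order of statements or options deals with position and does nothing about a key that runs in one direction. The design is a single cross-sectional survey with no comparison group or pre-letter baseline, so nothing nets out a tendency to agree.

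The effectiveness statement, made for a post-market commitment to FDA (Section 4), rests on six such items and one multiple-choice item. The fault lies in the instrument, so no later analysis can recover what was not asked.

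**Working it through.** **1. Q15a against its message (no assumption needed).**

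| Prescriber's view | Answer to Q15a | Scored | Holds the Section 5 message? |
|---|---|---|---|
| Use only above 200 units per day | True | Correct | Yes |
| Use above 200 and also at or below 200 | True | Correct | No |
| Not appropriate above 200 | False | Incorrect | No |

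The item separates only the third row from the rest. Q11 removes anyone who has not prescribed the pen, so the third group is likely to be small. The second row, which the word *only* is there to address, scores the same as the first.

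**2. The protocol's own figure.** Section 6.5 uses n = 200, 80% correct and N = 10,000. The half-width is 1.96 × √(0.8 × 0.2/200) × √(9,800/9,999) = 1.96 × 0.02828 × 0.9900 = 0.0549, or ±5.49 points, as stated. Precision is not the issue. The interval would be equally narrow around a biased proportion.

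**3. Effect of agreement on an item keyed True.** Let k be the share who know the message and a the share of the others who tick True (those who tick False or I don't know make up the remainder). Then

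observed proportion correct = k + (1 − k) × a.

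The documents give neither k nor a; both are assumptions. The majority rule is read as more than 100 of 200 correct, with the exact binomial tail.

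| k | a | Observed correct | Chance the rule is met |
|---|---|---|---|
| 40% | 0% | 40% | 0.002 |
| 40% | 25% | 0.40 + 0.60 × 0.25 = 55% | 0.91 |
| 40% | 50% | 0.40 + 0.60 × 0.50 = 70% | >0.99 |
| 20% | 25% | 0.20 + 0.80 × 0.25 = 40% | 0.002 |
| 20% | 50% | 0.20 + 0.80 × 0.50 = 60% | 0.997 |
| 20% | 75% | 0.20 + 0.80 × 0.75 = 80% | >0.99 |

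The expected proportion passes 50% once a exceeds (0.5 − k)/(1 − k): 0.1/0.6 = 17% when k = 40%, and 0.3/0.8 = 37.5% when k = 20%.

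**4. The extreme case, k = 0.** Let d be the share ticking I don't know and g the agreement rate among the rest. Observed correct is (1 − d) × g, and the expected proportion exceeds 50% only if d < 1 − 0.5/g.

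- g = 70%: d must be below 1 − 0.5/0.7 = 28.6%. At d = 29%, 0.71 × 0.7 = 49.7%, which falls short.
- g = 90%: d must be below 1 − 0.5/0.9 = 44.4%.
- g = 50% or less: not exceeded for any d.

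**5. What a mixed key changes.** A respondent who ticks True throughout scores 6/6 now. With an illustrative key of three True and three False, the score would be 3/6. Mixing the key balances a tendency to agree across items and makes it visible; it does not remove it from each item.

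**The case against.** On Q15a, the best defence is that the Prescriber Actions bullet of the letter also omits *only*. That does not rescue the item. Section 5 says its own messages will be tested, and there the restriction is explicit.

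On uniform keying, several points stand:

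- Respondents are not naive. Those mailed had prescribed the U-500 vial in the 12 months before launch (6.1), and the screener ends for anyone who has not prescribed the pen (Q11) or is not aware of having received the letter (Q14). A group with no knowledge is not the study population.
- I don't know is offered on every item and scored incorrect, which gives an unsure respondent an alternative to agreeing. It is a partial safeguard. A reader might infer that the items can only err upward; that is true of agreement alone, not of the endpoint as scored.
- Q15d and Q15f are phrased as negations and touch plausible misconceptions. Someone carrying over conversion from the vial should answer False to Q15d and be marked wrong, so these items can detect error even though agreement may inflate them.
- Q16, the seventh endpoint, includes an incorrect option, so ticking everything there fails. Q17 offers guessing, but as one of several tick-all choices for the whole set, so it gives a descriptive check and cannot correct any one item.
- A reader might see a contradiction with the non-leading claim in 6.10. Uniform keying and leading wording are different faults, and 6.10 claims randomisation only against positional bias. This is a weakness of design, not an inconsistency in the text.

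**Conclusion.** The Q15a point is established by the text alone. The first primary endpoint does not test the restriction in Section 5 and would score a prescriber who ignores it as correct. It must be corrected before fielding.

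The uniform key is a secondary weakness. Any tendency to agree raises percent correct on six of the seven primary endpoints, and the existing safeguards meet this only in part. Its size is unknown. Under the assumed 40% knowledge, agreement by a quarter of the others is enough to turn a likely failure of the majority rule (0.002) into a likely pass (0.91). This assumes that everyone who knows the message ticks True and that respondents answer independently; agreement may also differ between items.

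A reader might go further and infer that HCPs with no knowledge would pass every item. The documents do not support that. It needs particular values for both the agreement rate and the use of I don't know, neither of which is given, in a group that the screener is built to exclude.

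**What to change.** Before the user acceptance testing planned in 6.8:

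1. Reword Q15a so that a prescriber who would use the pen outside the restriction stated in Section 5 gives a different answer from one who would not.
2. Key some of the remaining Q15 items False, taking the key from the letter in Appendix I. Q15d and Q15f are natural candidates, because carry-over from vial conversion or click counting is plausible. The documents fix no particular number of reversed items; that is a design choice.
3. Update the endpoint list in 6.7.4 and the key in Appendix III to match. The click item needs editing in any case: 6.7.4 speaks of audibly verifying the dose, while Q15f speaks of determining it.

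Testing in 6.8 addresses comprehension and clarity, so clearly worded items would pass it with this fault intact. The rewording has to come first.

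The work is a few lines of survey text and programming. The sample size and the intervals in Table 1 do not change. The downside is that some HCPs will read a false safety statement, and the thank-you e-mail (6.2) corrects it only through a link they may not open. The correct answers could therefore also be shown on the closing screen once the survey is submitted, in keeping with the feedback that 6.10 already promises. The closing screen also serves screen failures, so this display should be limited to those who completed the survey.

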Appendix III Thank - You Letter and Correct Survey Responses

Dear [FIRST NAME] [LAST NAME]:

On behalf of Eli Lilly and Company, the maker of $Humulin^{@}R$ U-500 $KwikPen^{@}$, we want to thank you for taking part in the $Humulin_{@}R$ U-500 $KwikPen_{@}Survey$.

Additionally, to ensure that survey participants have accurate information about the risks of Humulin[®] R U-500 KwikPen[®], we have provided links to the following two documents:

- A copy of the correct answers to the survey questions about the Humulin® R U-500 KwikPen® key safety messages
- A copy of the Humulin[®] R U-500 KwikPen[®] Dear Health Care Provider (DHCP) letter.

<Insert the correct answers to the survey questions link>

<Insert DHCP letter link>

Sincerely,

The Humulin® R U-500 KwikPen® Survey Team

Correct Survey Responses to Humulin® R U-500 KwikPen®

15. Please answer True, False, or I don't know for each of the following statements regarding Humulin® R U-500 KwikPen®.

		True	False	I don't know
a	It is appropriate to prescribe Humulin [®] R U-500 KwikPen [®] to patients needing more than 200 units of	•	0	0
b	insulin per day. It is important to clearly specify the units of insulin (5-unit increments) on the prescription when prescribing Humulin [®] R U-500 KwikPen [®] .	•	0	0
c	When prescribing Humulin [®] R U-500 KwikPen [®] it is important to inform patients of their dose in units of insulin.	•	0	0
d	When administering the Humulin [®] R U-500 KwikPen [®] , patients do not need to convert the dose since the dose window shows the number of units to be injected.	-	0	0
e	It is important to instruct your patients that they should always have a backup Humulin [®] R U-500 KwikPen [®] available.	-	0	0
f	It is important to instruct your patients to not count clicks to determine their dose.		0	0

16. In the event of a Humulin[®] R U-500 KwikPen[®] malfunction, what would you instruct patients to do? (please select all that apply)

	U	se	a	bac.	kup	pen
--	---	----	---	------	-----	-----

[☐] Use a syringe to withdraw the insulin from the KwikPen®

[■] Contact a pharmacist or healthcare professional

[■] Contact The Lilly Answer Center for more information at [name]
